10.5.3. Primary Endpoint

The primary endpoint for this study is defined as follows: efficacy of cryoablation on local tumor control for each index tumor in patients with pulmonary metastatic disease at 12 months post cryoablation.

Patients are allowed up to 6 tumors and the primary efficacy endpoint (tumor control) will be calculated on a per tumor level. To be considered a success each tumor treated during the baseline procedure must meet the tumor control criteria at the 12 month follow-up visit.

The local tumor control counts and rates will be presented along with the 95% two-sided confidence intervals for the rates. The rate numerator will be defined as the number of tumors experiencing tumor control at 12-months. The rate denominator will be defined as the total number of tumors evaluated at 12-months.

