The primary efficacy endpoint for the trial is 12-month local control. The papers shown below were used as reference for clinicians who determined a clinically relevant efficacy endpoint performance goal was 84% success at 12-months. This observed cryoablation group's local control rate will be tested against this performance goal.

Paper	Lesions	12-month Local Control Success	Lower 97.5% 1-sided Wilson CI
Okuneiff (2006)	125	91%	0.8469
Rusthoven (2009)	63	100%	0.9425
Baschnagel (2013)	47	97%	0.8757
Ricardi (2012)	77	94%	0.8632
Norihisa (2008)	43	94.50%	0.8337
Yoon (2006)	101	90%	0.8261

This test is accomplished by testing against the following hypotheses:

$$H_0: C_{\text{DEVICE}} \leq 84.0\%$$

$$H_a: C_{\text{DEVICE}} > 84.0\%$$

where C_{DEVICE} is the observed cryoablation local control rate at 12-months.

The null hypothesis will be rejected and the primary efficacy endpoint performance goal will be met if the lower bound of the one-sided 97.5% confidence interval for the 12-month tumor local control rate is greater than 84.0%.

PASS 12 was used to calculate the sample size needed. A sample size of 203 lesions achieves 85% power (and guarantees at least 80% power) to detect a difference ($P_1 - P_0$) of 0.0700 using a one-sided binomial test. The target significance level is 0.0250. The actual significance level achieved by this test is 0.0239. These results assume that the population proportion under the null hypothesis is 0.8400.

Power Analysis of One Proportion

Numeric Results for testing $H_0: P = P_0$ versus $H_1: P > P_0$

Test Statistic: Exact Test

Power	N	Proportion		Target Alpha	Actual Alpha	Beta	Reject H_0 If $R \geq$ This
		Given H_0 (P_0)	Given H_1 (P_1)				
0.8501	203	0.8400	0.9100	0.0250	0.0239	0.1499	181

To account for up-to a 10% 12-month lesion attrition rate, the final sample size has been increased to 226 lesions.

Note that, for the purposes for sample size calculations, the observations are assumed to be independent. However, the primary analyses will account for within subject correlation, as described below.

General Analysis Methods

Data will be analyzed using descriptive statistics. Continuous variables (e.g., age) will be summarized by the number of patients, mean, standard deviation, median, interquartile range, minimum and maximum. Categorical variables (e.g., race) will be summarized by frequencies and percentages of patients in each category. 95% confidence intervals will be calculated as appropriate.

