Analysis Populations

All primary analyses will be performed on all tumors with a Galil Medical Cryoablation System and needles as the intent-to-treat evaluable population. A supplemental per-protocol analysis

will be done for the primary endpoint, removing tumors that 1) did not have a complete treatment; and subjects who 2) did not meet the study criteria but were enrolled; or 3) had a deviation with high likelihood of affecting the study outcome (as determined by a review of all occurring deviations).

The intent-to-treat and per-protocol analyses will be compared for level of agreement. It is expected that the two populations will be similar; however, any substantial differences between the two will be analyzed appropriately to elucidate the cause of these differences. Missing data will be imputed for the primary analysis as outlined in section "Handling of Missing Data" section later in the SAP. Additional sensitivity analyses using alternate missing data imputation will be presented.

Efficacy Endpoint Analysis

Efficacy Endpoint

The primary efficacy endpoint for this study is assessment of cryoablation on local tumor control in patients with pulmonary metastatic disease at 12 months post cryoablation.

Analysis Methods

The primary efficacy endpoint for this study is defined as follows: local tumor control in patients with pulmonary metastatic disease at 12 months post cryoablation. Tumor control will be defined by the criteria defined in Section 9.7 of this protocol.

Patients are allowed up to 6 tumors and the primary efficacy endpoint (tumor control) will be calculated on a per tumor level.

The rate of local tumor control at 12-months will be analyzed using a random effects logistic regression model accounting for within subject correlation to account for multiple tumors per subject. The null hypothesis will be tested comparing the lower bound of the Wald 97.5% one-sided confidence interval for the estimated rate of local tumor control to the performance goal of 84.0%. If the lower bound is greater than 84.0%, the null hypothesis will be rejected and the endpoint will be considered met.

Safety Endpoint Analysis

Safety Endpoint

The safety endpoint for this study is to assess the incidence and severity of cryoablation related adverse events.

Analysis Methods

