The safety endpoint for this study is to assess the incidence and severity of intra-operative events, post-operative adverse events, serious adverse events and unanticipated adverse device effects related to the cryoablation procedure.

No formal hypothesis test is being made on the safety endpoints. Point estimates and two-sided 95% confidence intervals will be generated for cryoablation related adverse events.

Supportive Endpoint Analyses

Tumor control (patient level & weighted average response)

The primary efficacy endpoint is on a lesion basis. Analysis on a patient level will also be conducted in two ways. 1) Patient level: A patient must exhibit tumor control on all lesions to be considered a success using logistic regression analysis to calculate success rate and Wald 95% CI. 2) Weighted average response: patient level response rate weighted by the number of lesions that are evaluated. This will be reported as a proportion (number of successful lesions over the total number of lesions) and a 95% exact CI.

Tumor control (pulmonary metastatic disease)

Efficacy of cryoablation on local tumor control in patients with pulmonary metastatic disease at 18 and 24 months post cryoablation using a random effects logistic regression model to account for the correlation among multiple tumors per subject.

Tumor control (additional cryoablation)

Patients may receive additional cryoablation treatment(s) to the index tumor(s) initially subjected to cryoablation while participating in the study protocol. This additional cryoablation may be performed on the index tumor(s) provided that the additional treatment is performed with Galil Medical technology. In this situation, for each index lesion retreated, follow-up visits will restart per the study protocol and continue through the 24 month visit after the date of the repeat cryoablation treatment. When possible, if multiple tumors are present, all efforts should be made to align all follow up visits. For any index lesion not subjected to retreatment, the data collection continues per protocol. If additional local treatment (e.g. radiofrequency ablation, microwave ablation, surgery, radiation) is required, then the patient must be withdrawn from the study.

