For the formal primary endpoint hypothesis test, patients with missing 12-month tumor evaluations will be imputed using multiple imputation (SAS PROC MI using FCS logistic regression and including tumor status at prior visits), except in the following case where previous visit evidence can be used to impute 12-month status:

- Subjects with local tumor failure at 6-months will be considered a local tumor failure at 12-months post-index procedure.

Additional sensitivity analyses to be conducted:

- Worst case: all missing data are imputed to be failures
- Best case: all missing data are imputed to be successes
- Complete case: all missing data are treated as missing and not imputed

Subset Analyses

Analysis will be done on outcomes for subgroups including, but not limited to, gender and lesion size. Additional non-protocol defined subgroups include: number of needles used, number of lesions, primary cancer diagnosis, and lesion location.

Poolability Analyses

A poolability analysis among investigational centers and geographies (US/OUS) will be performed for the primary efficacy endpoint. This analysis will be performed on the ITT population.

Poolability of Sites

Combining of Small Sites

Sites contributing less than 5 subjects to the as treated analysis set will be considered “small sites” and ordered by the date of first enrollment in the as treated analysis set. Starting with the first “small site”, a pseudo-site will be created by adding subjects from successive “small sites”. If the number of subjects reaches or exceeds the size of the median enrollment of the “large sites”, then a second pseudo-site will be created. Additional pseudo-sites, if needed, would be created in the same manner.

Primary Endpoint by Site

Among sites and pseudo-sites, the proportions of subjects who achieve local tumor control at 12 months will be compared using logistic regression. If the resulting p-value is ≤ 0.05 , further exploratory analysis will attempt to identify covariates (baseline characteristics) that may explain differences among the sites. Otherwise, the data will be considered to be poolable across study sites.

Poolability of Geographies

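### The primary test sets a Wald bound for an unspecified model-based rate against 84%; the choice of rate, scale and fitting method changes its type I error and power

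*SAP*

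**What the plan says.** The SAP (Efficacy Endpoint Analysis, Analysis Methods) takes the tumour as the unit. The 12-month control rate is to be "analyzed using a random effects logistic regression model accounting for within subject correlation", and the decision is made by "comparing the lower bound of the Wald 97.5% one-sided confidence interval for the estimated rate of local tumor control" with 84.0%. Nothing further is said about the model.

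The goal itself is a tumour-level proportion. Protocol 10.5.3 says "The rate numerator will be defined as the number of tumors experiencing tumor control at 12-months", and the denominator is the tumours evaluated at that time. The SAP's Sample Size Justification says that C_DEVICE "is the observed cryoablation local control rate at 12-months". It sizes the study with an exact binomial test on 203 tumours: "The actual significance level achieved by this test is 0.0239". It adds that "for the purposes for sample size calculations, the observations are assumed to be independent", while the primary analysis will allow for correlation within subjects.

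The SAP's Revision History records that the word exact was dropped from the interval because the random-effects model is the final test. A raw lesion proportion survives only as a supportive analysis: "This will be reported as a proportion (number of successful lesions over the total number of lesions) and a 95% exact CI". Protocol 10.1 still describes an exact one-sided 97.5% interval, and for a six-month closure rate. Under Handling of Missing Data, the SAP multiply imputes missing 12-month evaluations for the formal test but gives no rule for combining results across imputations. The Statistical Software section names SAS and no procedure for this model.

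**The concern.** A random-intercept logistic model has two natural rates. One is the inverse logit of the intercept, which is the rate for a patient whose random effect is zero. The other is the rate averaged over patients, which is the tumour-level rate in the population. They differ as soon as patients differ. A Wald bound can be built on the logit or the probability scale. The model can be fitted by quadrature or pseudo-likelihood, among other methods. With about 1.5 tumours per patient, the variance estimate will often be zero.

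The pass-or-fail verdict rests on this one bound, because the exact interval has been removed. If the choices stay open, they can be made after the data are seen, and some of them do not deliver the 2.5% error or 85% power on which the trial was sized.

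**Working it through.** **1. The plan's own figure.** Inputs from the SAP, Sample Size Justification: n = 203, p0 = 0.84, p1 = 0.91, reject at 181 or more.
- P(X ≥ 181 | 203, 0.84) = 0.0239
- P(X ≥ 181 | 203, 0.91) = 0.8501
- 203/0.9 = 225.6, rounded up to 226

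All three agree with the SAP.

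**2. Scale alone, independent tumours.** Let p = y/203 and z = 1.96.
- Probability scale: p − z·√[p(1−p)/203].
- Logit scale: inverse logit of {logit(p) − z/√[203·p(1−p)]}.

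At y = 180, p = 0.8867:
- Probability: 0.8867 − 1.96 × 0.02225 = 0.8431, which passes.
- Logit: 2.0575 − 1.96 × 0.2214 = 1.6235, giving 0.8353, which fails.

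At y = 181 the logit bound is 0.8409, which passes. At y = 179 the probability bound is 0.8374, which fails. The cut-offs are therefore:

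| Scale | Cut-off | Type I error | Power at 0.91 |
|---|---|---|---|
| Logit | 181 | 2.39% | 85.0% |
| Probability | 180 | 3.84% | 89.7% |

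**3. Which rate.** Take a normal patient effect on the logit scale with standard deviation SD, and solve for the intercept that makes the average rate over patients exactly 84%. The inverse-logit intercept is then 87.7% at SD 1, 90.7% at SD 1.5 and 93.3% at SD 2. The two rates coincide only at SD 0.

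**4. Clustered simulation.** The documents give neither the SD nor the number of tumours per patient, so both are assumed:
- SD 0/0.5/1/1.5/2.
- 134 patients and about 204 tumours.
- 1 to 6 tumours per patient with probabilities 68/20/7/3/1/1%.
- No missing data and no imputation.

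There were 8,000 trials per cell; the Monte Carlo SE is about 0.2 points near 2.5% and 0.6 near 50%. Type I error is taken at a true tumour-level rate of 84%, power at 91%. A zero variance estimate used the independent-tumour SE, and failed fits (at most 2.2%) counted as non-rejection. ML is maximum likelihood by quadrature.

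| Reading | Type I error, % | Power, % |
|---|---|---|
| ML averaged rate, logit | 1.8/2.2/2.0/2.2/2.4 | 80/80/78/76/73 |
| ML averaged rate, probability | 3.6/4.2/4.1/4.4/4.6 | about 7-9 points above the recommended rule |
| ML intercept, logit | 1.3/1.4/1.1/1.9/3.2 | 53/48/38/32/29 |
| ML intercept, probability | 4.6/6.5/14/34/56 | – |
| Pseudo-likelihood intercept, logit | 2.0/2.6/2.6/3.4/4.4 | 82-83 |

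On the same data, logit and probability bounds for the averaged rate disagree in 8-10% of trials at 91% and about 2% at 84%. The intercept and averaged-rate logit bounds disagree in 28-50% at 91%. A second, separately coded simulation (203 tumours, 800 trials per cell, SD 0/1/2) gave 55/37/25% power for the ML intercept with a logit bound. For the averaged rate with a logit bound it gave 1.5/3.2/2.1% type I error and 81/81/75% power. Its Monte Carlo SE near 2.5% is about 0.5 points.

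**5. Zero variance.** At a true 91% the SD estimate is zero in 60/52/33/19/10% of trials. For the averaged rate on the logit scale, switching those trials and failed fits to a GEE bound gives type I error 2.0/2.3/2.2/2.2/2.4% and power 81/82/79/76/73%. Against the first table row, that is at most 0.2 points of error and 2 of power.

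**6. Cluster mix.** With 204 tumours in 134 patients there are 204 − 134 = 70 extra tumours. At most five extra per patient means 70/5 = 14 to 70 multi-tumour patients. At those extremes (SD 0/1/2) the averaged-rate logit rule with fallback has type I error 2.3/2.6/2.3% and 2.0/2.1/2.1%, and power 81/76/70% and 84/81/76%. With about 228 evaluable tumours and the main mix, power is 86/84/78%.

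**The case against.** The fair defence is that the context already points to one reading. The endpoint is calculated per tumour, Protocol 10.5.3 defines tumours over tumours, and the SAP equates C_DEVICE with the observed rate. All of this favours the averaged rate, for which the remaining ambiguity costs one tumour at the pass mark, or about 2 points of type I error. The pseudo-likelihood logit bound is also mild: its 2.6% values are within simulation noise of 2.5%, and only 3.4-4.4% at SD 1.5-2 is a clear excess.

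A reader might infer from the table that the plan carries a 14-56% false-positive rate. The documents do not support that. Those figures come from testing the intercept while scoring error against the tumour-level rate. From SD 1 upward the intercept exceeds 84% when the tumour-level rate is 84%, so on its own terms the null is false. This is largely a change of estimand, and it depends on SDs that no document gives.

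A reader might also infer that the analysis fails without a zero-variance rule. For the averaged rate the fallback changes almost nothing.

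What stands is that the SAP never states the favoured reading. The inverse-logit intercept is the direct output of the model it names, and the scale stays open under either rate.

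**Conclusion.** The point holds as a gap in specification with measurable consequences. The part that needs no assumption about clustering is the scale: the same 180 successes in 203 pass or fail, and the probability scale has 3.84% type I error against a stated 2.5%.

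The rest is conditional on SD 0-2 and the assumed cluster mixes, with no imputation simulated. The averaged rate keeps about 2-2.5% on the logit scale and about 3.5-5% on the probability scale. The ML intercept does not estimate the rate behind the 84% goal. With a logit bound it has about 29-53% power. With a probability bound it rejects far above 2.5% at a tumour-level rate of 84% once SD reaches 1.

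The stated 85% power belongs to the exact test on independent tumours. Under the clustered rule recommended here it is roughly 70-84% with about 204 evaluable tumours, so the SAP's guarantee of at least 80% is not secured. Clustering is not the whole explanation: at SD 0 the rule has 81%, because the model still estimates a variance. The point should be fixed before analysis; it does not show that the trial's conclusion would be wrong.

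**What to change.** In the SAP's Analysis Methods for efficacy, state one rule:
- **Quantity tested:** the population-average tumour-level 12-month control rate.
- **Estimation:** random-intercept logistic model fitted by maximum likelihood with quadrature, integrated over the patient effect.
- **Bound:** one-sided 97.5% lower bound by the delta method on the logit scale, back-transformed and compared with 84%.
- **Imputation:** pool logit-scale estimates by Rubin's rules.
- **Zero variance or failed fit:** a rule named in advance, for example the logit-scale bound from an intercept-only GEE with patient-clustered robust variance. This is a safeguard with little effect on error or power.

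In Sample Size Justification, define C_DEVICE as this population rate. Say that 85% power applies to the exact test on independent tumours, and give roughly 70-84% for the clustered analysis with its assumptions (about 204 evaluable tumours, SD 0-2, assumed cluster mix, no imputation). In Protocol 10.1, replace the exact interval for a six-month closure rate with this 12-month test.

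The cost is a few sentences and slightly more programming, on the same data. The stated power becomes less favourable. The rule gives up about 7-9 points of power against the more liberal probability-scale bound on the same rate, and about 1-9 points against the pseudo-likelihood bound.

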13. SAFETY ASSESSMENTS

All adverse events (AEs), serious adverse events (SAEs) and unanticipated adverse device effects (UADEs) that occur within 30 days after the cryoablation procedure is performed will be recorded. The AEs, SAEs and UADEs identified within the first 30 days after the cryoablation procedure will be followed and reported until resolution.

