13.1. List of Definitions

Adverse Event (AE)

Any untoward or unfavorable medical occurrence in a human patient, including any abnormal sign (for example, abnormal physical exam or laboratory finding), symptom, or disease, temporally associated with the patient's participation in the research, whether or not considered related to the patient's participation in the research. All AEs must be recorded in the electronic database. A description of the event, including the start date, resolution date, action taken and the outcome should be provided, along with the investigator's assessment of the relationship between the AE and the study procedures.

The anticipated cryoablation related adverse events and their corresponding Common Terminology Criteria for Adverse Events (CTCAE) Terms are listed in Appendix B.⁴³

Serious Adverse Event (SAE)

Category 4 or higher of the CTCAE guidelines and the following ICH definitions will be used in the protocol as applicable.

- Results in Death

- Is Life Threatening

Note: The term 'life threatening' in the definition of serious refers to an event in which a patient was at immediate risk of death at the time of the event; it does not refer to an event which hypothetically might have caused death if it were more severe.

- Requires inpatient hospitalization or prolonged existing hospitalization

Note: Complications that occur during hospitalization are AEs. If a complication prolongs hospitalization or fulfills any other serious criteria, the event is serious. Hospitalization for elective treatment of a pre-existing condition that did not worsen from baseline is not considered to be an AE.

- Results in persistent or significant disability/incapacity

Note: The term disability means a substantial disruption of a person's ability to conduct normal life functions. This definition is not intended to include experiences of relatively minor medical significance (e.g., uncomplicated headache, nausea, vomiting, diarrhea, influenza, or accidental trauma) that may interfere or prevent everyday life functions, but do not constitute a substantial disruption.

- Results in permanent impairment of a body structure or body function or requires surgical intervention to prevent permanent impairment of a body structure or body function

- Leads to fetal distress, fetal death or a congenital anomaly/birth defect

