13.2. Causality Assessment

The investigator's assessment of causality must be provided for all adverse events (serious and non-serious). An investigator's causality assessment is the determination of whether there exists a reasonable possibility that the procedure and/or study device caused or contributed to an adverse event. If the investigator's final determination of causality is unknown and the investigator does not

know whether or not the procedure and/or study device caused the event, then the event will be handled as “related to procedure or study device” for reporting purposes. If the investigator’s causality assessment is “unknown but not related to procedure or study device,” this should be clearly documented on study records.

The investigator will evaluate AEs/SAEs/UADEs using the following guidelines:

- Description of event (if the event consists of multiple signs and symptoms, a diagnosis should be recorded rather than each sign and symptom)
 - Record term and grade according to the CTCAE 4.03 grading criteria
- Onset date
- Stop date
- Seriousness
 - The investigator must determine whether or not the AE meets the definition of serious as noted above and record in the eCRF. If the event is serious, the investigator must inform the Sponsor within 24 hours of knowledge of the event and complete the SAE report form.
- Relationship to Study Procedure and/or Study Device
 - The investigator must make a causality assessment for all AEs and decide whether there is a reasonable possibility the AE was caused by the procedure and/or study device.
 - If there is a valid reason to suspect a causal relationship between the AE and the procedure and/or study device, the AE should be considered “related or possibly related” to the procedure or study device.
- Outcome
- Action Taken

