16. STUDY COMMITTEE

16.1. Medical Monitor

An independent Medical Monitor will be designated to ensure the safety of patients throughout the duration of the study through regular review and analysis of the safety data. In the event the Medical Monitor and the Investigator disagree on adverse event analysis, an independent adjudicator will be retained for review and resolution.

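### The only adverse-event rates planned with confidence intervals cover events judged cryoablation-related; any-cause rates should stand beside them, and the attribution used should be stated

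*SAP*

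**What the plan says.** **What is collected.** Protocol 13 provides for recording "All adverse events (AEs), serious adverse events (SAEs) and unanticipated adverse device effects (UADEs) that occur within 30 days after the cryoablation procedure". Section 13.1 defines an adverse event without regard to causal relation and adds: "All AEs must be recorded in the electronic database".

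**What is estimated.** The SAP, under Safety Endpoint Analysis, sets the scope: "The safety endpoint for this study is to assess the incidence and severity of cryoablation related adverse events". Its methods paragraph continues: "Point estimates and two-sided 95% confidence intervals will be generated for cryoablation related adverse events". It also states: "No formal hypothesis test is being made on the safety endpoints". Protocol 5.2 and 10.5.4 carry the same restriction.

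**Who attributes.** Protocol 13.2 requires a causality call from the investigator for every event. Where a link is suspected, the event goes into a class that combines related and possibly related. Where causality finally remains unknown, "then the event will be handled as “related to procedure or study device” for reporting purposes". A different outcome is also allowed: "If the investigator’s causality assessment is “unknown but not related to procedure or study device,” this should be clearly documented on study records". Protocol 16.1 gives an independent Medical Monitor regular review of the safety data and adds: "In the event the Medical Monitor and the Investigator disagree on adverse event analysis, an independent adjudicator will be retained for review and resolution". The SAP (Randomization and Blinding) confirms that there is neither.

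**What is summarised without a relatedness filter.** Overall survival runs from the first procedure to death from any cause (Protocol 10.5.5 and the matching SAP section). The SAP also lists intra-operative complications (Additional Data Summaries) and a count of deaths (Subject Disposition).

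**The concern.** Safety is one of the two parts of the study objective (Protocol 4.1). An event reaches the planned estimate only after a judgement about its cause. That judgement is made first by someone who knows the treatment given, and no comparator arm exists in which under-attribution would show. Patients have Stage 4 disease. Several non-fatal events in Appendix B, such as respiratory failure, lung infection and thromboembolic event, could be put down either to the procedure or to the cancer.

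At stake is how the safety result can be read. From a related-only table, a reader cannot tell whether a low rate means few events or few attributions. Differences between sites in attribution would also be mixed into the rate. Protocol 10.4 includes safety in the poolability assessment, but the SAP's poolability section covers only the primary efficacy endpoint, so such differences would go unexamined.

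**Working it through.** **1. The plan's own figure.** There is none for safety: no expected rate, margin or power. The only sample-size calculation is for efficacy. It reproduces (exact binomial, 203 tumors, rejection at 181 or more: alpha 0.0239, power 0.8501; 203/0.9 = 225.6, rounded up to 226), and it has no bearing here.

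**2. Which events lack an unfiltered summary.**

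| Events | Planned summary | Limited to related events? |
|---|---|---|
| AEs and SAEs within 30 days | Point estimates with 95% intervals (SAP safety section; Protocol 10.5.4) | Yes |
| Intra-operative complications | Descriptive: number, type, severity (SAP Additional Data Summaries) | No |
| Deaths | Kaplan-Meier overall survival; count in Subject Disposition | No |
| Toxicities in interim reports | Frequency and severity; optional, no intervals stated (Protocol 10.5.6; SAP Interim Reporting) | Not stated |

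What remains exposed is chiefly non-fatal, post-operative AEs and SAEs. In the SAP sentence that lists the four event types, the words about relation to the procedure could grammatically qualify all four or only the last. The endpoint sentence and the interval sentence are not ambiguous: both are limited to related events.

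**3. Does the attribution procedure reach the analysis?** Three links are missing.
- The default for unknown causality in 13.2 is stated for reporting. The SAP does not repeat it.
- The SAP says only related. It does not say whether possibly related events count.
- Under 16.1, adjudication follows a disagreement. Neither document says that every relatedness call is re-reviewed, or that the adjudicated call is the one tabulated.

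**4. Direction.** Let A be the number of patients with at least one event of a given kind, and R the number with at least one such event judged related. R is a subset of A, so R/n ≤ A/n. With s = R/A, the related-only rate is s × (A/n).

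**5. Illustration on assumed inputs.** Take n = 150 (Protocol 5). Any-cause rates of 10%, 20% and 40%, and shares s of 90%, 75% and 50%, are assumptions. Neither document names the interval method for safety, so exact (Clopper-Pearson) limits are assumed: for x events, the lower limit is the 0.025 quantile of Beta(x, n−x+1) and the upper limit the 0.975 quantile of Beta(x+1, n−x). Counts are rounded to whole patients. For example, 0.75 × 30 = 22.5, taken as 23, and 23/150 = 15.3%.

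| Any-cause rate (95% CI) | s = 90% | s = 75% | s = 50% |
|---|---|---|---|
| 15/150 = 10.0% (5.7–16.0) | 14: 9.3% (5.2–15.2) | 11: 7.3% (3.7–12.7) | 8: 5.3% (2.3–10.2) |
| 30/150 = 20.0% (13.9–27.3) | 27: 18.0% (12.2–25.1) | 23: 15.3% (10.0–22.1) | 15: 10.0% (5.7–16.0) |
| 60/150 = 40.0% (32.1–48.3) | 54: 36.0% (28.3–44.2) | 45: 30.0% (22.8–38.0) | 30: 20.0% (13.9–27.3) |

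In three cells the upper limit lies below the any-cause rate: 16.0% against 20%, 38.0% against 40%, and 27.3% against 40%.

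**The case against.** The strongest reply is that procedure-related risk is a legitimate descriptive endpoint, stated in advance, and that no test or decision depends on it. An any-cause rate in Stage 4 patients includes disease events and overstates what the procedure does. The protocol also leans towards attribution. The threshold in 13.2 is a reasonable possibility that the procedure contributed, and unknown causality defaults to related. Appendix B lists respiratory failure, lung infection and thromboembolic event as anticipated, and 5.7 names embolus and infection as risks. An independent monitor reviews the data.

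All of that stands as a defence of keeping the related-only estimate. It does not supply an any-cause AE or SAE table, and it does not say whose call is analysed.

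A reader might also infer more than the documents support:
- *Early deaths could disappear from the report.* They could be missing from the related-event line, but overall survival and the death count would both show them.
- *Attribution rests with the site alone.* Section 16.1 provides independent review and adjudication.
- *Unknown but not related is a way to drop events.* It is a distinct judgement: the cause is unidentified, but the procedure is judged not to be it. Section 13.2 requires it to be documented.
- *The estimate must understate procedure risk.* The fixed direction holds only against the any-cause rate. Against true procedure-related risk, the defaults in 13.2 could push the estimate up.
- *Related-only rates cannot be set beside the cited series.* Two of the summaries in Protocol 3.2 themselves describe deaths as treatment or procedure related, and for the others the method of attribution cannot be seen.

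**Conclusion.** The point holds as a reporting gap. For non-fatal post-operative AEs and SAEs, the rate that will be published depends on attribution, and the SAP leaves open whose attribution and which causality classes count. That the rate cannot exceed the any-cause rate is certain. How far it falls short is not derivable from the documents. In the illustration, the shortfall runs from under 1 percentage point (10.0% shown as 9.3%) to 20 points (40% shown as 20%), depending wholly on the assumed rate and share. Nothing in the documents shows that investigators would under-attribute. The case for change is that the remedy is cheap and removes the dependence, not that bias has been demonstrated.

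**What to change.** In the SAP safety section:
1. Add patient-level any-cause AE and SAE rates within the 30-day window, by CTCAE grade, with 95% confidence intervals, for all patients in whom a procedure was started. Place them beside the related-only estimates, which stay.
2. State that related means the final attribution after review under Protocol 16.1.
3. State that possibly related and unknown causality count as related in the analysis, in line with Protocol 13.2.

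The category unknown but not related can remain, because those events will appear in the any-cause tables.

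The cost is SAP wording and one extra set of tables. No new data, visits or sample size are needed. The downside is that the any-cause rates will look less favourable and will include some events caused by the disease, which the text beside the tables should say.
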